- Study medication will be prescribed for thrice-daily administration and will be managed independent of PRN medications.

Study Procedures:

- Participants who are enrolled into the study will be randomized (stratified by sex, current morphine equivalent dose ($>100\text{mg}/\leq 100\text{mg}$), and Brief Pain Inventory Severity Scale ratings ($<7/\geq 7$)) to receive double-blind dose of buspirone (15mg, TID) or placebo. Buspirone will be purchased commercially and over-encapsulated to support blinding. In the event a participant leaves the unit prematurely (e.g., before completing the buspirone taper) he or she will be abruptly discontinued from buspirone.
- Participants will be asked to complete daily self-report ratings of opioid withdrawal severity (such as the Subjective Opioid Withdrawal Scale; SOWS) and to complete an exit survey that indicates whether they would recommend the medication to another person and the degree to which they believe the study medication helped them to successfully taper down on opioids and to which it suppressed their withdrawal symptoms.
- Participants will be permitted to stop taking the study medication at any time period and adherence will be collected and analyzed as a measure of acceptability.

- We will ask participants to refrain from requesting additional concomitant medications to help manage withdrawal symptoms until absolutely necessary. However, participants' requests for additional concomitant medication will be honored, and the day on which additional medication was requested will be recorded as a measure of efficacy (with the hypothesis that buspirone may delay the need for additional medications). Concomitant medications will be administered as part of the standard clinical practice and will not be provided by the study, though data regarding medication use will be collected for study outcome analyses. We believe this is the best approach for this initial study, as we cannot yet be certain that buspirone will reduce the severity of the withdrawal syndrome.

b. Study duration and number of study visits required of research participants.

Participants will be enrolled for the duration of their residential stay or 28 days, whichever comes first.

c. Blinding, including justification for blinding or not blinding the trial, if applicable.

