Participants in this study will be blinded to their study medication condition. This will provide the most rigorous test of this hypothesis and allow us to collect the strongest data with the smallest possible sample size. Since buspirone is not regularly administered for the treatment of opioid withdrawal, this blinding will not prevent participants from receiving their general standard-of-care treatment. We will also allow participants to request additional concomitant medications, consistent with standard care, and will track use of concomitant medications as an outcome measure.

d. Justification of why participants will not receive routine care or will have current therapy stopped.

N/A

e. Justification for inclusion of a placebo or non-treatment group.

A placebo control will be used to rigorously assess the study hypotheses, however buspirone is not currently used as a treatment for opioid withdrawal symptoms, therefore this placebo control will not prevent patients from otherwise receiving their standard of care treatment.

f. Definition of treatment failure or participant removal criteria.

Participants will be removed from the study if they withdraw consent, are unable to tolerate the medication, begin another medication that is contraindicated with buspirone, or are diagnosed with another condition for which buspirone treatment may be contraindicated.

g. Description of what happens to participants receiving therapy when study ends or if a participant's participation in the study ends prematurely.

Participants can choose to participate and withdraw consent later with no consequences; any participant who withdraws consent will continue to receive standard-of-care opioid tapering resources as part of their primary treatment. Participants who wish to continue buspirone treatment following study completion will be referred to their physician for continued care.

5. Inclusion/Exclusion Criteria

Inclusion Criteria: Be 18 years or older and undergoing a taper from their opioid medications

Exclusion Criteria: Being pregnant or breastfeeding, past 7-day use of grapefruit juice or other strong CYP P450 inhibitors, have no clinically significant chronic medical or surgical disorders or conditions that are judged by the investigators to be contraindicated with buspirone administration, or have current suicidality as assessed by clinic staff or the Columbia Suicide Severity Rating Scale (C-SSRS).

6. **Drugs/ Substances/ Devices**

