- a. The rationale for choosing the drug and dose or for choosing the device to be used.

Oral buspirone (Buspar) will be tapered up to a total daily dose of 45mg. This dose has shown previous efficacy in reducing opioid withdrawal symptoms in patients being tapered off the long-acting opioid methadone²⁷ and will be replicated here as pilot data to support an NIH grant application. Participants in this study may request to not take a dose and the reason for this will be documented and treated as primary outcome data.

Buspirone is generally administered twice daily, based upon early reports indicating multiple daily dosing was effective for reducing anxiety (relative to diazepam) and based upon cited but not published open-range dose finding study⁴⁵. A meta-analysis subsequently reported equivalent anxiety treatment outcomes and adverse events profiles with BID vs. TID dosing⁴⁶. Early studies reported a greater incidence of dysphoria and dizziness following 20mg buspirone dosing relative to smaller doses^{45,47,48}. Though the incidence of adverse events was lower with 20mg buspirone than the diazepam comparison, this result appears to have shaped the current practice of multiple daily dosing. A subsequent evaluation of side effects among 700 patients receiving a mean 20mg buspirone reported no difference in the rate of side effects as compared to placebo and fewer side effects relative to diazepam and clorazepate⁴⁹.

Buspirone has only 4% bioavailability and is eliminated quickly and primarily by first-pass metabolism-with less than 1% of an oral dose being excreted as unchanged drug and 60% of metabolites being excreted in urine⁵⁰. The elimination half-life of an oral dose is 2.5 hours and this does not change as a function of the dose administered⁵⁰. Buspirone serum levels increase in a linear manner with dosing. Plasma levels of buspirone increase quickly after ingestion, achieving Cmax within an hour of dosing and Tmax within 60-84 minutes^{50,51}. Human laboratory studies indicate that buspirone doses and area-under-the-curve values are linear up to QD 40mg dose (which was the highest dose tested)⁵¹ indicating that bioavailability is proportional to the dose administered. A multi-dose administration study that provided healthy volunteers with 10mg doses every 12 hours for 10 days reported no accumulation of buspirone or its metabolites⁵².

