- b. Justification and safety information if FDA approved drugs will be administered for non-FDA approved indications or if doses or routes of administration or participant populations are changed.

Buspirone is FDA-approved for the treatment of anxiety disorder and can be prescribed off-label for other indications. Consistent with our study procedures, the FDA permits a maximum of 60mg to be administered per day in divided doses.

- c. Justification and safety information if non-FDA approved drugs without an IND will be administered.

N/A

7. Study Statistics (Partially Blinded)

a) Primary outcome variable.

i. Feasibility

- a. Participant retention in treatment, evaluated as a) last day in the study and b) being present on the final day of the study

ii. Initial Efficacy

- a. Withdrawal symptom suppression, measured through daily self-report ratings of withdrawal on the Subjective Opiate Withdrawal Scale (SOWS)

b) Statistical plan including sample size justification and interim data analysis.

- a) Sample size: This is a pilot study to support an R01 trial. A power analysis using G-power, evaluating an independent groups t-test of area-under-the-curve (AUC) values from the SOWS, with alpha set to 0.05, revealed that 12 participants per group would yield 60% (moderate) power to detect a large (0.80) effect. We believe this will provide sufficient data to support an R01 study evaluation.

- b) Statistical Plan. Given the small sample size and low perceived risk, no interim data analyses will be conducted.

1. Feasibility

- i. Patient retention in treatment will be compared across groups using independent groups t-tests for continuous and chi-squares for dichotomous outcomes. Regressions factoring group, baseline opioid dose in morphine equivalents, pain severity ratings from the Brief Pain Inventory, and number of concomitant medications, and study medication adherence (% prescribed doses) will be used to determine the degree to which group assignment predicted being retained on the final scheduled day (Logistic) and final day in treatment (Linear).

2. Initial Efficacy

- i. Withdrawal symptom suppression will be compared across groups using area-under-the-curve (AUC) analyses.

c) Early stopping rules.

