Review of the literature on buspirone suggests that reported buspirone discontinuation effects pertain to the reemergence of depression and/or anxiety for which the buspirone was prescribed. We can find no published evidence of a buspirone-specific withdrawal syndrome aside from this effect. Further, the majority of research regarding reemergence effects refers to extended buspirone exposure (>6 weeks), which is significantly longer than what is proposed here. Since we cannot find evidence of a buspirone-specific withdrawal syndrome, are not prescribing buspirone for anxiety or depression, and are administering it for a relatively short period of time, we do not believe this study puts participants at undue risk of experiencing buspirone-specific withdrawal symptoms.

b. Steps taken to minimize the risks.

The biggest risk incurred by buspirone administration is that it is consumed with contraindicated medication and/or alcohol, and this risk is mitigated in this study because participants will only be consuming buspirone under staff observation while residing on a closed clinical unit. We will also exclude or wait to enroll any participant who has consumed any contraindicated medications (including CYP3A4 inhibitors or inducers) or grapefruit juice in the previous 7 days to further prevent any drug interactions from occurring. Any participant who experiences adverse effects of the study medication will be permitted to stop taking the medication or to remain at the dose at which they felt comfortable and this decision will be made jointly with the study physician and participant. Finally, there is a risk that participants who decide to discharge themselves from treatment will abruptly discontinue their buspirone dosing without benefit of a dose taper period. There is a chance that participants could experience a mild and transient dysphoria following abrupt discontinuation. We will inform all patients about the risk associated with abrupt discontinuation of the study medication prior to study enrollment, so they will be able to make an informed choice regarding whether they want to participate in the study. Given the very brief duration for which participants will receive buspirone, we expect that any discontinuation syndrome that is experienced will be mild and of short duration.

c. Plan for reporting unanticipated problems or study deviations.

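### The retention regressions adjust the group effect for study-drug adherence and concomitant-medication count, both of which follow from treatment, so the group coefficient is not the effect of assignment.

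*Combined protocol and SAP*

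**What the plan says.** Section 7a names retention as the primary feasibility outcome, measured as the last day in the study and as presence on the final day. Section 7b (1. Feasibility) gives it two analyses.

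- **Unadjusted.** Retention "will be compared across groups using independent groups t-tests for continuous and chi-squares for dichotomous outcomes".
- **Regression.** The first predictors are listed as "Regressions factoring group, baseline opioid dose in morphine equivalents, pain severity ratings from the Brief Pain Inventory". The sentence then adds two more and states the aim: "number of concomitant medications, and study medication adherence (% prescribed doses) will be used to determine the degree to which group assignment predicted" retention. A logistic model handles presence at the scheduled end and a linear model handles the last treatment day.

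Elsewhere the protocol treats the last two covariates as results of the trial:

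- **Adherence.** In section 4a, "adherence will be collected and analyzed as a measure of acceptability". In section 6a, participants "may request to not take a dose and the reason for this will be documented and treated as primary outcome data". Section 8b adds: "Any participant who experiences adverse effects of the study medication will be permitted to stop taking the medication".
- **Concomitant medication.** In section 4c, the investigators "will track use of concomitant medications as an outcome measure". In section 4a, the day of the first request is an efficacy measure, "with the hypothesis that buspirone may delay the need for additional medications".

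**The concern.** The stated purpose of the regressions is to show how far assignment predicts retention. That requires covariates that assignment cannot affect. If buspirone eases withdrawal, and so reduces medication requests and keeps people on the unit, holding the request count fixed removes part of the benefit being measured. If buspirone's side effects lower adherence, comparing participants at equal adherence sets unlike people against each other and can create or enlarge a difference. Withdrawal severity plausibly drives both covariates and retention, so the two distortions can act together.

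The retention result may support an R01 application. If the regression and the unadjusted test disagree, nothing in the plan says which one is the finding.

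**Working it through.** The plan gives no figure for these regressions; its only power figure concerns withdrawal-score AUC. The check therefore covers timing, then definition, then size under stated assumptions.

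**1. Timing.** Adherence as a percentage of prescribed doses exists only after randomisation. The word baseline is attached only to opioid dose. The medication count has no time window, but sections 4a and 4c use the term for medication requested during the stay, so on-study use is the natural reading. If a pre-randomisation count was meant, that half of the point falls and the adherence half stands.

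**2. Adherence denominator.** Three doses a day (section 4a) for 28 days (section 4b) is 3 × 28 = 84 doses. A fully adherent participant who leaves after day 14 has taken 3 × 14 = 42.
- Against the full schedule: 42/84 = 50%.
- Against doses due while enrolled: 42/42 = 100%.

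On the first reading adherence cannot exceed last day/28, so the covariate partly restates the outcome of the linear model.

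**3. Linear model (all coefficients assumed).** Let g be group, U an unmeasured severity factor, and every error term (e) and U have unit variance:
- withdrawal W = U − a·g + e
- concomitant use C = W + e
- adherence A = −0.5W − d·g + e
- retention R = −W + b·g + e

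Here a is benefit through withdrawal, b is direct benefit, and d is adherence lost on drug.

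Within arm, Var(W) = 2, Var(C) = 3, Var(A) = 1.5, Cov(C,A) = −1, Cov(C,R) = −2 and Cov(A,R) = 1. Solving 3β_C − β_A = −2 and −β_C + 1.5β_A = 1 gives β_C = −4/7 and β_A = 2/7.

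The group effects are a + b on R, −a on C and 0.5a − d on A. The adjusted coefficient is

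(a + b) − (4/7)a − (2/7)(0.5a − d) = b + (2/7)(a + d).

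| a, b, d | True effect | Adjusted |
|---|---|---|
| 0.8, 0, 0 | 0.80 | 0.229 (29%) |
| 0.8, 0, 0.2 | 0.80 | 0.286 (36%) |
| 0.4, 0.4, 0.2 | 0.80 | 0.571 (71%) |
| 0, 0.8, 0 | 0.80 | 0.800 (100%) |
| 0, 0.8, 0.8 | 0.80 | 1.029 (129%) |
| 0, 0, 0.8 | 0 | 0.229 |

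The 0.80 is in model units. The within-arm SD of R is √3, so it equals 0.80/1.732 = 0.46 SD, not the standardised 0.80 in the plan's power statement.

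With 24 participants and 20,000 simulated trials per scenario (two-sided 0.05), rejection rates unadjusted against adjusted are:
- 19% against 8% at (0.8, 0, 0.2)
- 19% against 40% at (0, 0.8, 0.8)
- about 5% against 6.6% in the null case (0, 0, 0.8)

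**4. The sign can change.** Take a second assumed model with a direct effect of 0.20. The drug lowers adherence by 0.5, and adherence raises retention by 0.5 per unit. The true effect is 0.20 − 0.5 × 0.5 = −0.05, while the adjusted coefficient is 0.20.

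**5. Day-level model (assumed).** The daily leaving hazard is 0.010 with a hazard ratio of 0.55 and stay capped at 28 days, so about 76% and 86% are retained and the true effect is 1.50 days. The drug changes length of stay only. Median adherence is 75% or 90% (between-person logit SD 0.5 to 1.5), with 0.5 medication requests a day (log SD 0.5 to 1.0). Share of the true effect kept after adjustment:
- per-day medication rate, doses-due adherence: 100%
- cumulative count, doses-due adherence: 84% to 97%
- per-day medication rate, full-28-day adherence: 6% to 68%

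So when the drug affects neither adherence behaviour nor the request rate, the definitions alone decide whether the coefficient is distorted.

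**The case against.** The strongest reply is that retention is already compared properly. The unadjusted tests come first and are the only analyses described as comparing groups, so the regressions can be read as supporting models in a 24-person pilot. This stands as a limit on scope: the fault is confined to the regressions. It does not remove it, because the regressions are given the explicit purpose of showing how far assignment predicts retention and no analysis is ranked above the other.

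Second, doses after departure are not naturally prescribed, since enrolment ends with the stay. That favours the doses-due denominator, and the 6% to 68% range belongs only to the other reading. This is fair, but the plan does not say so, and choosing doses due does not cure the bias in step 3.

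Third, section 4a hypothesises a later first request, not fewer medications, and section 6a treats the reasons for refused doses, not the adherence percentage, as primary outcome data. Both are literally correct. Section 4c nevertheless makes concomitant use itself an outcome, and section 4a does the same for adherence.

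Fourth, all magnitudes are assumed and none was computed for the logistic model. Both are true. Some settings give no bias, for instance when assignment affects neither covariate and neither depends on length of stay, but the plan cannot guarantee them.

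Finally, at 12 per arm with 76% and 86% retained, about 12 × 0.24 + 12 × 0.14 = 4.6 leavers are expected. The chi-square approximation is then doubtful and any multi-covariate logistic model is fragile. That comes from the plan's choice of tests at this size; the change proposed here neither causes nor cures it.

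**Conclusion.** The concern holds. As written, the group coefficient in the retention regressions does not estimate the effect of assignment, because the models condition on adherence, which is certainly post-randomisation, and on a concomitant-medication count that is post-randomisation on the natural reading. That conclusion rests on the text alone.

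The size and direction cannot be derived from the documents. The assumed scenarios show shrinkage, inflation, a spurious effect under the null and a change of sign. The unadjusted comparisons by randomised group are not affected by this fault. Because a named primary outcome is involved and the plan does not say which analysis governs, this should be fixed before analysis.

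**What to change.** Replace the regression wording in section 7b (1. Feasibility) with text to this effect:

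- The main retention analysis is the unadjusted comparison by randomised group: t-test for last day, chi-square for presence on the final day.
- Supporting regressions contain group and baseline variables only: sex, baseline morphine equivalents and baseline Brief Pain Inventory severity.
- Concomitant-medication count and study-medication adherence are reported by arm as outcomes.

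If a model with those two variables is kept, label it exploratory and state that its group coefficient is not read as the effect of assignment. Define in advance the time window of the count and the adherence denominator (doses due while enrolled, or all scheduled doses).

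The cost is two or three sentences. No new data are needed: the three baseline variables are the stratification factors in section 4a, and adherence and medication use are already collected.

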first week of entering the Pain Treatment Unit located in the Johns Hopkins Hospital. The goals of the study are to collect initial feasibility and efficacy data to support a NIH grant application.

Study Enrollment: During the first week of their residential stay, patients who meet initial eligibility criteria will be informed of the study by their attending physician or other clinic staff member. Patients who are interested in the study will review and sign the informed consent with a trained study staff member before completing the Screening. To increase generalizability, the Screening process will be very limited and restricted to collecting baseline data regarding opioid withdrawal severity and information to characterize the sample. Participants will also be asked to provide authorization for the study to access their medical records to allow documentation of additional concurrent medications and retention in treatment.

Standard of Care Taper Procedures:

- This study will be run concurrent with the standard taper that is administered in the Pain Treatment Unit. The study will not dictate the terms of the taper, however (if our hypothesis is correct) it is possible that the taper may occur more quickly in patients who are treated with buspirone. Information regarding the taper will be retrieved from the medical records and evaluated as outcome data.
- The tapering protocol is individualized to the patient but follows the same standard rationale. Patients are generally stabilized on their admitting medications to ensure they have informed the staff their correct usage. They are then converted to a long-acting formulation such as Oxycontin (if not already on one) and a standing schedule of dosing is implemented (e.g., q6 hours). In most cases, the opioid dose is decreased by 10-20% every 3 days, and withdrawal symptoms and pain are monitored. The speed and magnitude decrease of the taper is adjusted based upon the results of those ongoing assessments in order to optimize patient participation in the treatment plan. The goal is to completely taper the patient off opioids by the end of 28 days, though this may vary depending on the individual circumstances of the patient. Additional PRN concomitant medications are also made available via standing orders to help manage symptoms of withdrawal (e.g., nausea, diarrhea, muscle aches and pains). Medications are available upon patient request.

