Participants will be discharged from the study if they leave the residential unit against medical advice, request to be removed from the study, begin taking a medication that is contraindicated with participation, are diagnosed with a contraindicated condition, express suicidal thoughts, or if new information becomes available to suggest this study may cause them more than minor harm.

8. Risks

- a. Medical risks, listing all procedures, their major and minor risks and expected frequency.

Buspirone (Buspar) is an oral tablet that is FDA-approved for the treatment of anxiety and prescribed off-label for the treatment of depression. It has been prescribed at doses up to 90mg/day for depression. The maximum dose provided to participants in this study (45mg/day) is well within the range of approved doses and is below the maximum dose recommended for the treatment of anxiety (60mg/day). Buspirone is rated as pregnancy category B, indicating that animal studies have not indicated a unique risk of buspirone on the

developing fetus but that controlled human studies have not yet been conducted. We will exclude all women who are pregnant or breastfeeding from participating. When administered orally (as proposed here) buspirone effects peaks in 40-90 minutes. It has 90% bioavailability and 86% protein binding. It is subject to extensive first-pass metabolism by the P450 CYP3A4 enzymes, and produces active metabolites. The elimination half-life is 2-3 hours, and this is prolonged in patients with impaired hepatic or renal function.

Buspirone is excreted in both fecal (18-38%) and renal (29-63%) waste, though renal excretion is primarily as metabolites. Buspirone is contraindicated with severe hepatic or renal impairment, and has several severe drug interactions with alcohol, MAOIs, and grapefruit juice (all of which will be excluded).

Recognized side effects include nausea (8%), dizziness (12%), headache (6%), somnolence (10%), and feeling nervous (5%). Potential serious side effects include congestive heart failure (less than 0.1%), myocardial infarction (less than 0.1%), and cerebrovascular accident (less than 0.1%).

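### The SOWS AUC is not scaled for days observed and has no rule for missed or post-exit days; computed as a plain total it would mix daily withdrawal severity with length of stay

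*Combined protocol and SAP*

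**What the plan says.** Section 7a lists withdrawal suppression, measured by daily SOWS ratings, as the initial-efficacy primary outcome. The analysis (section 7b, Initial Efficacy) reads in full: "Withdrawal symptom suppression will be compared across groups using area-under-the-curve (AUC) analyses". The sample-size paragraph of 7b adds the test: "evaluating an independent groups t-test of area-under-the-curve (AUC) values from the SOWS", with 12 per group, an effect of 0.80, alpha 0.05 and 60% power.

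Follow-up is not fixed. Section 4b: "Participants will be enrolled for the duration of their residential stay or 28 days, whichever comes first". Section 4f: "Participants will be removed from the study if they withdraw consent, are unable to tolerate the medication". Section 7c: "Participants will be discharged from the study if they leave the residential unit against medical advice, request to be removed from the study". No SOWS collection after exit is described.

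Retention is itself a primary outcome (section 7a): "Participant retention in treatment, evaluated as a) last day in the study and b) being present on the final day of the study". It is compared between arms in 7b: "Patient retention in treatment will be compared across groups using independent groups t-tests for continuous and chi-squares for dichotomous outcomes". Section 4a also says that "it is possible that the taper may occur more quickly in patients who are treated with buspirone".

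No section divides the AUC by days observed or gives a rule for missed ratings or for days after exit.

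**The concern.** Each day with a SOWS score above zero adds area. A plain AUC over observed days is therefore roughly mean daily severity times days observed, and it answers a mixed question. Someone who leaves early with bad withdrawal can score lower than someone who stays to day 28 with mild withdrawal.

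Three things follow for a comparison of daily severity:

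- Early exits add variation unrelated to daily severity, so they cost power even when the arms are balanced.
- If buspirone improves retention, its extra rated days raise its AUC and can hide a benefit.
- If buspirone patients are followed for less time, for instance through removal for intolerance, their AUC falls and can exaggerate a benefit.

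SOWS AUC is the only efficacy measure with a stated analysis and is the basis of the sample size. Its result is meant to support the R01 application, so a distorted estimate would carry forward. Two analysts following the present text could also compute different outcomes from the same ratings.

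**Working it through.** **1. The plan's own figure.** Inputs from section 7b: n = 12 per group, d = 0.80, alpha 0.05. Noncentral t with df = 22 and noncentrality 0.80 × √(12/2) = 1.96. One-sided power is 60.0%, which matches the plan; two-sided power is 46.6%. The plan does not state sidedness, which is a separate matter. The two-sided figure is the reference below.

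**2. Break-even arithmetic.** Suppose daily SOWS is 20% lower on buspirone and all buspirone patients stay 28 days. The plain totals are equal when placebo averages 0.80 × 28 = 22.4 days. That needs 4 of 12 placebo patients to leave near day 11: (8 × 28 + 4 × 11.2)/12 = 268.8/12 = 22.4.

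**3. Assumptions for the simulations.** The documents give no SOWS values or exit rates. Assumed: placebo mean 18 per day, between-person SD 8, within-person SD 5, constant severity over time, exits uniform on days 4-24 (mean day 14), everyone else rated to day 28. An effect of d = 0.8 is about 0.8 × 8 = 6.4 points per day, so buspirone averages 11.6.

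**4. Expected plain totals.**

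- Complete data: 18 × 28 = 504 v 11.6 × 28 = 324.8, a difference of 179.2.
- Exits 4 placebo v 1 buspirone: mean days (8 × 28 + 4 × 14)/12 = 23.33 and (11 × 28 + 14)/12 = 26.83. Totals 18 × 23.33 = 420 v 11.6 × 26.83 = 311, a difference of about 109. The contrast is 39% smaller with no change in daily severity.
- No true effect, exits 1 v 4: 18 × (26.83 − 23.33) = 63 points in favour of buspirone.

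The per-day mean difference is unchanged in all three.

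**5. Simulated power at d = 0.8** (3,000 trials per scenario, two-sided t-test):

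| Exits (placebo v buspirone) | Plain AUC | AUC per observed day |
|---|---|---|
| None | 46% | 46% |
| None, stays uniform 21-28 days | 45% | 46% |
| 3 v 3 | 34% | 46% |
| 4 v 1 | 17% | 46% |
| 1 v 4 | 61% (inflated) | 46% |

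For 4 v 1 the plain-AUC figure runs from 27% to 4% as the assumed mean goes from 12 to 30.

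**6. No true effect, exits 1 v 4.** Plain AUC favours buspirone in about 7% of trials and placebo in about 0.2%, so total error is about 7% against a nominal 5%. The per-day AUC favours buspirone in 2.2-2.5%, as it should. With exits 1 v 2, plain AUC favours buspirone in 2.7%, which is essentially no inflation.

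**7. Would the planned retention tests give warning?** In the example of step 2 (4 v 0 exits), yes: chi-square p = 0.028, t-test p = 0.028. With 4 v 1 exits, mostly not: chi-square p = 0.13, and the last-day t-test is significant in only about 1% of simulated trials.

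**8. Limit of the per-day AUC.** If severity rises by 16 points over the stay and exits are 4 v 1, per-day AUC power is 33% against 46% for a mixed model of the daily ratings. With the same rise and balanced 3 v 3 exits, per-day AUC keeps 44%.

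**The case against.** The strongest reply is that the text never says the AUC is a plain total. A time-averaged AUC is compatible with it, so this is an unspecified summary in a 24-person pilot, not a demonstrated wrong analysis. That stands, and the point is worded conditionally.

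A reader might go further than the documents allow in five ways.

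- *The plan has no time horizon at all.* Not so. Section 4b caps participation at 28 days, section 7b refers to a scheduled final day, and the payments in section 10 imply (400 − 120)/10 = 28 rated days. What is missing is the treatment of shorter follow-up.
- *Any difference in stay biases the AUC.* Only relative to mean daily severity. A plain total measures cumulative burden, and if withdrawal and stay both ended sooner, a smaller total would be a real gain. The protocol does not say which quantity it wants.
- *A false claim of benefit is as serious a risk as a missed one.* Under the assumptions used, total error rises only to about 7% even with 1 v 4 exits. Lost power and a distorted estimate are the main harms.
- *A quicker taper on buspirone will shorten the stay.* Section 4a raises a quicker taper but does not link it to earlier discharge.
- *Exit will depend on withdrawal severity.* The only support is a background statement about treatment for opioid use disorder. Here tapers are adjusted to symptoms, as-needed medication is available and ratings are paid, all of which could weaken that link.

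The planned retention tests are a partial answer. They would reveal a gross imbalance, but they can miss a smaller one and they correct nothing.

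**Conclusion.** The point holds in conditional form and should be fixed. The omission is certain: no scaling and no missing-day rule appear anywhere, while follow-up varies and retention is an outcome that may differ by arm. The direction of the distortion under a plain total follows from arithmetic, given scores above zero. Its size does not: power of 34% or 17% in place of 46%, and false-positive error of about 7% in place of 5%, rest on assumed exit patterns and SOWS values. If stays vary only between 21 and 28 days the loss is about 1 point and the matter is minor.

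**What to change.** Replace the efficacy sentence in section 7b with wording such as:

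> SOWS AUC over study days 1-28 will be divided by the number of days observed (mean daily SOWS) and compared between groups by t-test. Missed ratings within the stay will be interpolated; days after exit or discharge will be left missing, not set to zero. Days observed will be shown by group beside the SOWS result.

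Add a linear mixed model of the daily ratings as a sensitivity analysis, because a per-day AUC can still be biased when severity changes over the taper and exits differ by arm. Making the mixed model primary is not needed: with constant severity the two have the same simulated power (46%), and its day 1-28 contrast extrapolates past planned discharge.

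The cost is a few sentences and a little programming. Daily SOWS and last day are already collected, and the t-test on an AUC keeps the sample-size basis. The downsides should be stated: a per-day mean does not measure total withdrawal burden and does not remove bias from severity-related exit, and the mixed model assumes data are missing at random.
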